Clinical Chemistry and Hematology								X							X													X	X	X
Pregnancy Test ^f								X							X													X	X	X

Page 1 of 2

Footnotes are defined on the last page of the table.

Table 2-4. Phase 1b Schedule of Activities – Extended Dosing Period Subjects Only (Week 105 Through Week 158)

	Visits for weekly dosing	TREATMENT PERIOD ^a																											PD Visit	SFU/ EOS ^b				
		Visits for weekly and biweekly dosing																																
Study Week	105,107,109,111, 113,115,117,119, 121,123,125,127, 129,131,133,135, 137, 139, 141, 143, 145,147,149,151, 153,155,157	106	108	110	112	114	116	118	120	122	124	126	128	130 ^c	132	134	136	138	140	142	144	146	148	150	152	154	156	158	Any-time					
PHARMACOKINETIC AND ANTIBODY ASSESSMENTS																																		
OTHER																																		
Lymphocyte Subsets ^k																																		
Biomarker Development Sample ^k																																		
DOSE																																		
Weekly Efavaleukin Alfa Administration ^l		X	X	X	X	X	X	X	X	X	X	X	X	X	X	X	X	X	X	X	X	X	X	X	X	X	X	X	X	X				
Biweekly Efavaleukin Alfa Administration ^l			X	X	X	X	X	X	X	X	X	X	X	X	X	X	X	X	X	X	X	X	X	X	X	X	X	X	X	X				

Page 2 of 2

CRF = case report form; cGVHD = chronic graft versus host disease; ECG = electrocardiogram; EOS = end of study for individual subject; EOET = end of extended treatment; GVHD = graft versus host disease; NIH = National Institutes of Health; PD = progressive disease; PFT = pulmonary function test; PK = pharmacokinetics; Q2W = every 2 weeks; QW = every week; [REDACTED]; [REDACTED]; SFU = safety follow-up

Subjects in the extended dosing period who discontinue treatment prior to week 258 (Q2W dosing) or week 259 (QW dosing) for any reason will complete an EOET visit and 6-weeks of safety follow-up after the last dose of efavaleukin alfa. See [Table 2-6](#).

^a Subjects who withdraw early from treatment will complete the EOET visit and Safety follow-up visit within a window of \pm 7 days of the next regularly scheduled visit after the last dose of efavaleukin alfa, consisting of all assessments included in the week 260 visit.

^b Safety follow-up visit will be done 6 weeks (\pm 3 days) after the last dose of efavaleukin alfa. Women of childbearing potential will be required to complete a pregnancy test at this visit.

^c Re-assessment of subject's response to efavaleukin alfa treatment will be conducted every 6 months and a decision may be made by the Sponsor, following discussion and agreement between the principal investigator and medical monitor, to allow subjects who wish to, to continue treatment through week 258 (Q2W dose) or week 259 (QW dose).

^d A single ECG will be collected prior to blood draws or other invasive procedures. See Section [9.2.3.3](#).

^e Record steroid use and/or changes to dose on concomitant medication CRF page.

^f A 2 or 6 minute walk test is optional for the NIH Form A assessment.

^g PFTs (spirometry) will be used in the NIH Form A assessment unless the subject is unable to comply. PFTs must be obtained at the Baseline visit unless they were performed at the Screening visit. Thereafter PFTs are strongly preferred at all visits which include the NIH Form A assessment and must be performed for all subjects who have an abnormal PFT at Baseline, who have known pulmonary GVHD or who have new pulmonary symptoms. If PFTs cannot be performed as part of the NIH Form A assessment, the lung symptom score should be substituted.

For women of childbearing potential, on study pregnancy tests are urine.

^h Doses of investigational product in phase 1b must be given within \pm 3 days from the scheduled visit for subjects in Q2W dosing and \pm 2 days from the scheduled visit for QW dosing. Subjects will remain at the site for at least 30 minutes following doses of investigational product. Once [REDACTED] has been selected, investigational product will be administered within \pm 2 days.

Table 2-5. Phase 1b Schedule of Activities – Extended Dosing Period Subjects Only (Week 159 Through Week 222)

	Visits for weekly dosing	TREATMENT PERIOD ^a																									PD Visit	SFU/ EOS ^b			
		Visits for weekly and biweekly dosing																													
Study Week	159,161,163,165, 167,169,171,173, 175,177,179,181, 183,185,187,189, 191,193,195,197, 197,199,201,203, 205,207,209,221	160	162	164	166	168	170	172	174	176	178	180	182 ^c	184	186	188	190	192	194	196	198	200	202	204	206	208 ^c	210	222	Any-time		
GENERAL ASSESSMENTS																															
Physical Examination																														X	
Vital Signs	X	X	X	X	X	X	X	X	X	X	X	X	X	X	X	X	X	X	X	X	X	X	X	X	X	X	X	X	X		
Weight																		X											X		
ECG ^d																		X											X	X	
CLINICAL OUTCOME ASSESSMENTS																															
LABORATORY ASSESSMENTS																															
Clinical Chemistry and Hematology						X									X													X		X	X
Pregnancy Test ⁱ						X									X												X		X	X	

Page 1 of 2

Footnotes are defined on the last page of the table.

Table 2-5. Phase 1b Schedule of Activities – Extended Dosing Period Subjects Only (Week 159 Through Week 222)

	Visits for weekly dosing	TREATMENT PERIOD ^a																									PD Visit	SFU/ EOS ^a			
		Visits for weekly and biweekly dosing																													
Study Week	159,161,163,165, 167,169,171,173, 175,177,179,181, 183,185,187,189, 191,193,195,197, 197,199,201,203, 205,207,209,221	160	162	164	166	168	170	172	174	176	178	180	182	184	186	188	190	192	194	196	198	200	202	204	206	208	210	222	Any-time		
PHARMACOKINETIC AND ANTIBODY ASSESSMENTS																															
OTHER																															
Lymphocyte Subsets ^k																														X	
Biomarker Development Sample ^k																														X	
DOSE																															
Weekly Efavaleukin Alfa Administration ^l	X	X	X	X	X	X	X	X	X	X	X	X	X	X	X	X	X	X	X	X	X	X	X	X	X	X	X	X			
Biweekly Efavaleukin Alfa Administration ^l		X	X	X	X	X	X	X	X	X	X	X	X	X	X	X	X	X	X	X	X	X	X	X	X	X	X	X			

Page 2 of 2

CRF = case report form; cGVHD = chronic graft versus host disease; ECG = electrocardiogram; EOS = end of study for individual subject; EOET = end of extended treatment; GVHD = graft versus host disease; NIH = National Institutes of Health; PD = progressive disease; PFT = pulmonary function test; PK = pharmacokinetics; Q2W = every 2 weeks; QW = every week; [REDACTED] [REDACTED] SFU = safety follow-up

Subjects in the extended dosing period who discontinue treatment prior to week 258 (Q2W dosing) or week 259 (QW dosing) for any reason will complete an EOET and 6-weeks of safety follow-up after the last dose of efavaleukin alfa. See [Table 2-6](#).

^a Subjects who withdraw early from treatment will complete the EOET visit and Safety follow-up visit, within a window of \pm 7 days of the next regularly scheduled visit after the last dose of efavaleukin alfa, consisting of all assessments included in the week 260 visit

^b Safety follow-up visit will be done 6 weeks (\pm 3 days) after the last dose of efavaleukin alfa. Women of childbearing potential will be required to complete a pregnancy test at this visit.

^c Re-assessment of subject's response to efavaleukin alfa treatment will be conducted every 6 months and a decision may be made by the Sponsor, following discussion and agreement between the principal investigator and medical monitor, to allow subjects who wish to, to continue treatment through week 258 (Q2W dose) or week 259 (QW dose).

^d A single ECG will be collected prior to blood draws or other invasive procedures. See [Section 9.2.3.3](#).

^e Record steroid use and/or changes to dose on concomitant medication CRF page.

^f A 2 or 6 minute walk test is optional for the NIH Form A assessment.

^g PFTs (spirometry) will be used in the NIH Form A assessment unless the subject is unable to comply. PFTs must be obtained at the Baseline visit unless they were performed at the Screening visit. Thereafter PFTs are strongly preferred at all visits which include the NIH Form A assessment and must be performed for all subjects who have an abnormal PFT at Baseline, who have known pulmonary GVHD or who have new pulmonary symptoms. If PFTs

[REDACTED]
For women of childbearing potential, on study pregnancy tests are urine.

[REDACTED]
e
scheduled visit for QW dosing. Subjects will remain at the site for at least 30 minutes following doses of investigational product. Once [REDACTED] has been selected, investigational product will be administered within \pm 2 days.

Table 2-6. Phase 1b Schedule of Activities – Extended Dosing Period Subjects Only (Week 223 Through Week 260)

	Visits for weekly dosing	TREATMENT PERIOD ^a																				PD Visit	SFU/ EOS ^b		
		Visits for weekly and biweekly dosing																							
Study Week	223,225,227,229, 231,233,235,237, 239,241,243,245, 247,249,251,253, 257,259	224	226	228	230	232	234 ^c	236	240	242	244	246	248	250	252	254	256	258	260/ EOET ^d	Any-time					
GENERAL ASSESSMENTS																									
Physical Examination																									
Vital Signs	X	X	X	X	X	X	X	X	X	X	X	X	X	X	X	X	X	X	X	X	X	X	X		
Weight							X														X	X			
ECG ^e							X														X	X	X		
Concomitant Medication	X	X	X	X	X	X	X	X	X	X	X	X	X	X	X	X	X	X	X	X	X	X	X		
Corticosteroid use ^f	X	X	X	X	X	X	X	X	X	X	X	X	X	X	X	X	X	X	X	X	X	X	X		
Adverse Events	X	X	X	X	X	X	X	X	X	X	X	X	X	X	X	X	X	X	X	X	X	X	X		
Serious Adverse Events	X	X	X	X	X	X	X	X	X	X	X	X	X	X	X	X	X	X	X	X	X	X	X		
Disease-Related Events	X	X	X	X	X	X	X	X	X	X	X	X	X	X	X	X	X	X	X	X	X	X	X		
NIH cGVHD Response Assessment (NIH Form A) ^g							X														X	X			
Pulmonary Function Test ^h							X														X	X			
CLINICAL OUTCOME ASSESSMENTS																									
LABORATORY ASSESSMENTS																									
Clinical Chemistry and Hematology							X									X					X		X		X
Pregnancy Test ⁱ							X								X					X		X		X	

Page 1 of 2

Footnotes are defined on the last page of the table.

Table 2-6. Phase 1b Schedule of Activities – Extended Dosing Period Subjects Only (Week 223 Through Week 260)

	Visits for weekly dosing	TREATMENT PERIOD ^a																			PD Visit	SFU/ EOS ^a	
		Visits for weekly and biweekly dosing																					
Study Week	223,225,227,229, 231,233,235,237, 239,241,243,245, 247,249,251,253, 257,259	224	226	228	230	232	234	236	240	242	244	246	248	250	252	254	256	258	260/ EOET	Any-time			
PHARMACOKINETIC AND ANTIBODY ASSESSMENTS																							
OTHER																							
Lymphocyte Subsets ^b								X													X	X	
Biomarker Development Sample ^c								X													X		
DOSE																							
Weekly Efavaleukin Alfa Administration ^d	X	X	X	X	X	X	X	X	X	X	X	X	X	X	X	X	X	X	X	X	X		
Biweekly Efavaleukin Alfa Administration ^e		X	X	X	X	X	X	X	X	X	X	X	X	X	X	X	X	X	X	X	X		

Page 2 of 2

CRF = case report form; cGVHD = chronic graft versus host disease; ECG = electrocardiogram; EOS = end of study for individual subject; EOET = end of extended treatment; GVHD = graft versus host disease; NIH = National Institutes of Health; PD = progressive disease; PFT = pulmonary function test; PK = pharmacokinetics; Q2W = every 2 weeks; QW = every week; [REDACTED]; SFU = safety follow-up

^a Subjects who withdraw early from treatment will complete the EOET visit and Safety follow-up visit within a window of \pm 7 days of the next regularly scheduled visit after the last dose of efavaleukin alfa, consisting of all assessments included in the week 260 visit.

^b Safety follow-up visit will be done 6 weeks (\pm 3 days) after the last dose of efavaleukin alfa. Women of childbearing potential will be required to complete a pregnancy test at this visit.

^c Re-assessment of subject's response to efavaleukin alfa treatment will be conducted every 6 months and a decision may be made by the Sponsor, following discussion and agreement between the principal investigator and medical monitor, to allow subjects who wish to, to continue treatment through week 258 (Q2W dose) or week 259 (QW dose).

^d Subjects in the extended dosing period who discontinue treatment prior to week 258 (Q2W dosing) or week 259 (QW dosing) for any reason will complete an EOET visit and 6-weeks of safety follow-up after the last dose of efavaleukin alfa.

^e A single ECG will be collected prior to blood draws or other invasive procedures. See Section 9.2.3.3.

^f Record steroid use and/or changes to dose on concomitant medication CRF page.

^g A 2 or 6 minute walk test is optional for the NIH Form A assessment.

[figure not shown]
^h PFTs (spirometry) will be used in the NIH Form A assessment unless the subject is unable to comply. PFTs must be obtained at the Baseline visit unless they were performed at the Screening visit. Thereafter PFTs are strongly preferred at all visits which include the NIH Form A assessment and must be performed for all subjects who have an abnormal PFT at Baseline, who have known pulmonary GVHD or who have new pulmonary symptoms. If PFTs cannot be performed as part of the NIH Form A assessment, the lung symptom score should be substituted.

^j For women of childbearing potential, on study pregnancy tests are urine.

^m Doses of investigational product in phase 1b must be given within \pm 3 days from the scheduled visit for subjects in Q2W dosing and \pm 2 days from the scheduled visit for QW dosing. Subjects will remain at the site for at least 30 minutes following doses of investigational product. Once [REDACTED] has been selected, investigational product will be administered within \pm 2 days.

[figure not shown]
Product: Efavaleukin Alfa
Protocol Number: 20160283
Date: 22 June 2021

Page 40 of 148

[figure not shown]
Product: Efavaleukin Alfa
Protocol Number: 20160283
Date: 22 June 2021

Page 41 of 148

Product: Efavaleukin Alfa
Protocol Number: 20160283
Date: 22 June 2021

Page 42 of 148

[figure not shown]

Product: Efavaleukin Alfa
Protocol Number: 20160283
Date: 22 June 2021

Page 43 of 148

[figure not shown]
Product: Efavaleukin Alfa
Protocol Number: 20160283
Date: 22 June 2021

Page 44 of 148

[figure not shown]
Product: Efavaleukin Alfa
Protocol Number: 20160283
Date: 22 June 2021

Page 45 of 148

[figure not shown]
Product: Efavaleukin Alfa
Protocol Number: 20160283
Date: 22 June 2021

Page 46 of 148

Product: Efavaleukin Alfa
Protocol Number: 20160283
Date: 22 June 2021

Page 47 of 148

3. Introduction

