CRF = case report form; cGVHD = chronic graft versus host disease; ECG = electrocardiogram; EOS = end of study for individual subject; EOT = end of therapy; GVHD = graft versus host disease; NIH = National Institutes of Health; PBMC = peripheral blood mononuclear cell; PD = progressive disease; PFT = pulmonary function test; PK = pharmacokinetics; Q2W = every 2 weeks; SFU = safety follow-up

^a Subjects who withdraw early from treatment will complete the EOT visit and Safety follow-up visit **within a window of \pm 7 days of the next regularly scheduled visit after the last dose of efavaleukin alfa, consisting of all assessments included in the week 52 visit.**

^b Safety follow-up visit will be done 6 weeks (\pm 3 days) after the last dose of efavaleukin alfa. Women of childbearing potential will be required to complete a pregnancy test at this visit.

^c At the discretion of the Sponsor, following discussion and agreement between the principal investigator and medical monitor, subjects responding to efavaleukin alfa (as assessed by the end of week 50), who wish to continue treatment, will complete week 52 assessments and may continue to receive efavaleukin alfa treatment at their current dosing regimen for up to an additional 52 weeks (see [Table 2-3](#)). The remaining subjects will complete the week 52/EOT visit and 6-weeks of safety follow-up after the last dose of efavaleukin alfa.

^d A single ECG will be collected prior to blood draws or other invasive procedures. See Section [9.2.3.3](#).

^e Record steroid use and/or changes to dose on concomitant medication CRF page.

^f A 2 or 6 minute walk test is optional for the NIH Form A assessment.

^g For subjects on biweekly dosing arm, beginning at week 18, subjects come in for biweekly visits.

^h PFTs (spirometry) will be used in the NIH Form A assessment unless the subject is unable to comply. PFTs must be obtained at the Baseline visit unless they were performed at the Screening visit. Thereafter PFTs are strongly preferred at all visits which include the NIH Form A assessment and must be performed for all subjects who have an abnormal PFT at Baseline, who have known pulmonary GVHD or who have new pulmonary symptoms. If PFTs cannot be performed as part of the NIH Form A assessment, the lung symptom score should be substituted.

For women of childbearing potential, on study pregnancy tests are urine.

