	372,386,400,414, 428,442,456,470, 484,498,512,526, 540,554,568,582, 596,610,624,638, 652,666,680,694, 708,722	379	393	407	421	435	449	463	477	491	505	519	533	547	561	575	589	603	617	631	645	659	673	687	701	715	729		
CLINICAL OUTCOME ASSESSMENTS																													
LABORATORY ASSESSMENTS																													
Clinical Chemistry and Hematology					X		X		X		X		X		X		X		X		X		X		X		X		X
Pregnancy Test ^f				X		X		X		X		X		X		X		X		X		X		X		X		X	
PHARMACOKINETIC AND ANTIBODY ASSESSMENTS																													
OTHER																													
Lymphocyte Subsets ^l						X			X			X			X			X			X			X			X		
Biomarker Development Sample ^l						X			X			X			X			X			X			X			X		
DOSE																													
Weekly Efavaleukin Alfa Administration ^m	X	X	X	X	X	X	X	X	X	X	X	X	X	X	X	X	X	X	X	X	X	X	X	X	X	X	X	X ⁿ	
Biweekly Efavaleukin Alfa Administration ^m		X	X	X	X	X	X	X	X	X	X	X	X	X	X	X	X	X	X	X	X	X	X	X	X	X	X	X ⁿ	

CRF = case report form; cGVHD = chronic graft versus host disease; ECG = electrocardiogram; EOS = end of study for individual subject; EOET = end of extended treatment; GVHD = graft versus host disease; NIH = National Institutes of Health; PD = progressive disease; PFT = pulmonary function test; PK = pharmacokinetics; Q2W = twice weekly; QW = every week; [REDACTED]; SFU = safety follow-up

^a Subjects who withdraw early from treatment will complete the EOET visit and Safety follow-up visit within a window of \pm 7 days of the next regularly scheduled visit after the last dose of efavaleukin alfa, consisting of all assessments included in the week 104 visit.

^b Safety follow-up visit will be done 6 weeks (\pm 3 days) after the last dose of efavaleukin alfa. Women of childbearing potential will be required to complete a pregnancy test at this visit.

^c Re-assessment of subject's response to efavaleukin alfa treatment will be conducted at week 76 and a decision may be made by the Sponsor, following discussion and agreement between the principal investigator and medical monitor, to allow subjects who wish to, to continue treatment through week 102 (Q2W dose) or week 103 (QW dose).

^d Subjects in the extended dosing period who discontinue treatment prior to week 258 (Q2W dosing) or week 259 (QW dosing) for any reason will complete an EOET visit and 6-weeks of safety follow-up after the last dose of efavaleukin alfa.

^e A single ECG will be collected prior to blood draws or other invasive procedures. See Section 9.2.3.3.

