9.1.4 End of Treatment

Subjects discontinuing treatment prior to week 52 for any reason (see Section [8.1](#)) will be asked to complete an End of Treatment visit within a window of \pm 7 days of the next regularly scheduled visit after the last dose of efavaleukin alfa, consisting of all assessments included in the week 52 visit according to the Schedule of Activities (see [Table 2-2](#)). If the End of Treatment visit for a subject occurs $<$ 7 days after a progressive

disease visit, then the procedures completed at the End of Treatment visit should only be those NOT performed at the progressive disease visit.

For phase 1b subjects participating in the extended dosing period, subjects discontinuing treatment prior to week **102** or week **103** will be asked to complete the EOET visit within a window of + 7 days of the next regularly scheduled visit after the last dose of efavaleukin alfa, consisting of all assessments included in week **104** visit according to the Schedule of Activities (see [Table 2-3](#)). Subjects continuing treatment after week **104** but discontinuing treatment before week **258** (Q2W dosing) or week **259** (QW dosing) will be asked to complete an EOET visit within a window of \pm 7 days of the next regularly scheduled visit after the last dose of efavaleukin alfa, consisting of all assessments included in the week **260** visit according to the Schedule of Activities (see [Table 2-6](#)). If the EOET visit for a subject occurs < 7 days after a progressive disease visit, then the procedures completed at the EOET visit should only be those NOT performed at the progressive disease visit.

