9.1.5 Safety Follow-up/End of Study

Upon completion of the treatment period or permanent discontinuation from the study treatment for any reason, a safety follow-up visit will be performed approximately 6 weeks (\pm 3 days) after the last dose of efavaleukin alfa as described in the Schedule of Activities (see [Table 2-1](#), [Table 2-2](#), [Table 2-3](#), [Table 2-4](#), [Table 2-5](#), [Table 2-6](#), [Table 2-7](#), and [Table 2-8](#)). Women of childbearing potential will be required to complete a pregnancy test at this visit.

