9.2.3.1.1 Time Period and Frequency for Collecting and Reporting Safety Event Information

9.2.3.1.1.1 Disease-related Events

Disease-related events are defined in [Appendix 4](#).

The investigator is responsible for ensuring that all disease-related events observed by the investigator or reported by the subject that occur after the first dose of investigational product through the safety follow-up visit/end of study are recorded using the Event CRF.

All serious disease-related events will be recorded and reported to the sponsor or designee within 24 hours. The investigator will submit any updated serious disease-related event data to the sponsor within 24 hours of it being available.

Disease-related events assessed by the investigator to be more severe than expected and/or related to the investigational product(s)/study treatment/protocol-required therapies, and determined to be serious, must be reported on the Event CRF as serious adverse events and recorded and reported per Section [9.2.3.1.1.3](#) and [Appendix 4](#).

Disease-related events pre-defined for this study are listed in [Appendix 11](#).

9.2.3.1.1.2 Adverse Events

The adverse event grading scale to be used for this study will be the CTCAE version 4.03 and is described in [Appendix 4](#).

The investigator is responsible for ensuring that all adverse events observed by the investigator or reported by the subject that occur from first dose of investigational product through the safety follow-up visit/EOS are reported using the Event CRF.

9.2.3.1.1.3 Serious Adverse Events

The investigator is responsible for ensuring that all serious adverse events observed by the investigator or reported by the subject that occur after signing of the informed consent through safety follow-up visit/EOS are reported using the Event CRF.

All serious adverse events will be collected, recorded and reported to the sponsor or designee within 24 hours, as indicated in [Appendix 4](#). The investigator will submit any updated serious adverse event data to the sponsor within 24 hours of it being available.

The criteria for grade 4 in the CTCAE grading scale differs from the regulatory criteria for serious adverse events. It is left to the investigator's judgment to report these grade 4 abnormalities as serious adverse events.

9.2.3.1.1.4 Serious Adverse Events After the Protocol-required Reporting Period

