### **Treatment Emergent AE (TEAE)**

A treatment emergent adverse event is any adverse event categorized as adverse events starting on or after first dose of investigational product as determined by "Did event start before first dose of investigational product" equal to "No" or missing on the Events eCRF and up to and including 42 days after the last dose of investigational product excluding events reported after End of Study date on eCRF form, whichever is earlier.

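### Footnote a of Tables 2-1 to 2-6 gives early withdrawers' safety follow-up visit a timing that cannot be met together with the 6 weeks stated in footnote b and Section 9.1.5

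*Protocol*

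**What the plan says.** **Footnote a, Tables 2-1 to 2-6.** It is addressed to subjects who stop treatment early. In Tables 2-1 and 2-2 it begins "Subjects who withdraw early from treatment will complete the EOT visit and Safety follow-up visit"; in Table 2-3 such subjects "will complete the EOET visit and Safety follow-up visit within a window of \pm 7 days of the next regularly scheduled visit" after the last dose. Tables 2-4 to 2-6 say the same in substance. The footnote ends by giving the content as that of the week 52, 104 or 260 visit, depending on the table.

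**Footnote b, same tables.** "Safety follow-up visit will be done 6 weeks (\pm 3 days) after the last dose of efavaleukin alfa".

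**Other places that give 6 weeks.**
- Protocol Section 9.1.5, on completion of treatment or permanent discontinuation for any reason: "a safety follow-up visit will be performed approximately 6 weeks (\pm 3 days) after the last dose of efavaleukin alfa".
- The schema text in Protocol Section 2.1, for all subjects.
- Footnote d of Tables 2-3 and 2-6, on discontinuers in extended dosing, who "will complete an EOET visit and 6-weeks of safety follow-up after the last dose of efavaleukin alfa".
- SAP Section 5.2, Safety Follow-up/End of Study Visit.

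**Places that tie the ±7-day window to the end-of-treatment visit alone.** Under Protocol Section 9.1.4, subjects stopping before week 52 "will be asked to complete an End of Treatment visit within a window of \pm 7 days of the next regularly scheduled visit", with no mention of the safety follow-up visit. SAP Section 5.2, End of Treatment Visit, does the same.

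**What depends on the visit.** Protocol Section 9.2.3.1.1.2 requires adverse events "that occur from first dose of investigational product through the safety follow-up visit/EOS are reported using the Event CRF". The SAP counts treatment-emergent events "up to and including 42 days after the last dose of investigational product", and leaves out those reported after the End of Study date if that comes earlier. SAP Section 5.2 sets a subject's End of Study date at the last completed protocol-specified procedure.

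**The concern.** Two adjacent footnotes give the same visit two timings, and a site cannot satisfy both for a subject who stops early. Footnote a speaks to early withdrawers by name, so a coordinator could take it as the special rule and footnote b as the general one.

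The visit closes adverse-event collection, and adverse-event incidence is a primary phase 1b endpoint. If the visit were held with the end-of-treatment visit and no later procedure followed, the End of Study date could also fall early and shorten the treatment-emergent window. SAP Appendix G would not show this, because it keeps the safety follow-up visit under its scheduled label and applies no day window to it.

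The subjects concerned are not a random subset. They include anyone with a DLT (Protocol Section 7.4.1.2), treatment failures (Section 7.4.2.1.1) and those stopping for adverse events (Section 8.1). The pregnancy test attached to the visit would move with it.

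**Working it through.** This is calendar arithmetic, counted in days after the last dose.

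**Inputs**
- Safety follow-up under footnote b and Section 9.1.5: 6 weeks ±3 days.
- Footnote a: next scheduled visit ±7 days.
- Visit spacing: 7 days for QW cohorts. For Q2W cohorts, weekly visits at first, then two-weekly from week 18 (Table 2-2 footnote g).
- Visit windows after week 4: ±2 days for QW, ±3 days for Q2W (Protocol Section 9.1.2).
- SAP treatment-emergent window: 42 days.

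**Step 1. Is 6 weeks the figure the rest of the plan uses?**
- 6 × 7 = 42 days, equal to the SAP window.
- Protocol Section 5.3.2 gives maximum participation of about 14 months, or 62 with extended dosing. With a month of 365.25/12 days: 28 + 52 × 7 + 42 = 434 days = 14.3 months, and 28 + 260 × 7 + 42 = 1,890 days = 62.1 months. Both agree.

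**Step 2. When does each footnote place the visit?**
- Footnote b: 42 − 3 = 39 to 42 + 3 = 45.
- Footnote a, nominal timing: (spacing − 7) to (spacing + 7).
- Footnote a, latest day if the last dose was given early within its visit window: spacing + 7 + 2 or + 3.

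| Situation | Footnote a, nominal | Latest with visit window | Earliest under footnote b | Smallest gap, nominal | Smallest gap with visit window |
|---|---|---|---|---|---|
| QW | day 0 to 14 | 7 + 7 + 2 = 16 | 39 | 39 − 14 = 25 | 39 − 16 = 23 |
| Q2W, weekly visits before week 18 | day 0 to 14 | 7 + 7 + 3 = 17 | 39 | 25 | 39 − 17 = 22 |
| Q2W, two-weekly visits | day 7 to 21 | 14 + 7 + 3 = 24 | 39 | 39 − 21 = 18 | 39 − 24 = 15 |

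The two windows do not overlap in any row.

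**Step 3. Where does the arithmetic stop applying?** It assumes regular spacing. The tables as printed skip some weeks: Table 2-5 lists nothing between weeks 210 and 221, and Table 2-6 has no week 238 or 255. These gaps may be slips, but the bounds above do not hold there.

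**The case against.** The strongest reply is that the plan already answers the question and footnote a is the only outlier.

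- The schema text deals with early discontinuation for any reason. For the extended period it gives the ±7-day window to the EOET visit, and it then requires the 6-week safety follow-up visit of all subjects.
- Sections 7.4.2.1.1 and 9.1.3 send treatment failures and subjects with progressive disease to Section 9.1.5.
- Most table headers tag the treatment period with a and the safety follow-up column with b.
- The closing clause of footnote a describes the content of the week 52, 104 or 260 visit, which cannot be the safety follow-up visit because that has its own column.
- In Tables 2-1 and 2-2 the window clause is in bold. If bold marks amended text, the clause was inserted into an older sentence that named both visits, and subjects who withdrew earlier were never under it.

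All of this stands as evidence of intent. It does not remove a sentence, repeated in six tables, that says otherwise.

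Two mitigations also stand in part. Serious events that the investigator learns of after the reporting period must still be reported regardless of causality (Section 9.2.3.1.1.4), although the SAP definition could keep them out of the treatment-emergent tables, and non-serious events have no such provision. The analysis is descriptive, with no statistical hypothesis in phase 1b (SAP Section 2.2), so no test is affected.

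A reader might infer that the plan deliberately gives early withdrawers a shorter safety follow-up, that sites will close these subjects at the end-of-treatment visit, or that late events are being lost selectively. The documents do not support this. Every other passage on the timing gives 6 weeks, nothing instructs a site to merge the visits and close the subject, and nothing shows that any site did so.

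**Conclusion.** Footnote a is wrong as written, because it contradicts footnote b, the schema text, Section 9.1.5 and SAP Section 5.2 on the timing of the safety follow-up visit. It is probably a drafting slip.

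The consequence is conditional. If a site followed footnote a, the visit would come at least 25 days (weekly visits) or 18 days (two-weekly visits) before the earliest day that footnote b allows on nominal timing, and at least about 22 or 15 days before it once visit windows are counted. Collection of non-serious adverse events, and possibly the End of Study date, could then stop before day 42.

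It is tempting to turn this into a fixed share of the 42-day window lost by every early withdrawer. That is not supported: the figures rest on regular visit spacing, on the site choosing footnote a over footnote b, and on no later procedure setting the End of Study date. How many subjects were affected, if any, cannot be known from the documents. The point still merits correction, because it touches the follow-up period for a primary endpoint in the subjects who stopped treatment early.

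**What to change.** Reconcile footnote a of Tables 2-1 to 2-6 with footnote b and with Protocol Sections 9.1.4 and 9.1.5, so that each visit has one stated timing. Splitting footnote a does this: one statement gives the window and content of the EOT/EOET visit, and a separate one covers the safety follow-up visit. Once that is settled, check that adverse-event collection and the SAP treatment-emergent window cover the same days. Which timing is kept is for the sponsor to decide; none is proposed here.

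The SAP says the study is ending early (Sections 1 and 10), so a wording change may reach few remaining subjects. The final analysis should therefore also report days from last dose to End of Study for early withdrawers, so that any shortened follow-up can be seen.

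The cost is a footnote edit, a short note to sites with subjects still on study, and one descriptive summary from dates already collected. No visit is added.
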